5.1.2 DOSING AND ADMINISTRATION

Families in both groups receive home visits with their home visitors at least monthly, but in most cases two home visits are completed per month. Due to the COVID-19 pandemic, some home visits may need to be completed remotely by telephone or video calls. Information on the frequency of completed home visits (dates of completed visits) and type of visit (in-person or remote visit) will be documented by home visitors as part of their standard home visiting responsibilities.

Home visitors randomized to the HABITS intervention group will be instructed to contact their families weekly between home visits by text, telephone, or video call to briefly check-in with the caregiver about how they are doing with their HABIT and work with the caregiver (as needed) to briefly problem-solve challenges. Home visitors will be instructed to document the date and type (text, telephone, video call) of every check-in completed with families.

5.2 MEASURES TO MINIMIZE BIAS: RANDOMIZATION

Randomization will be at the level of the home visitors (cluster randomization). Home visitors (n=18) will be randomly assigned to deliver the home visiting standard curriculum with HABITS (n=9 home visitors) or without HABITS (n=9 home visitors). The likelihood of bias related to cluster randomization (i.e., by home visitors) is reduced because all mothers are low-income with a relatively equal number of African American and White mothers. To reduce the risk of contamination between treatment arms, the training and supervisions of home visitors assigned to each arm of the trial will be conducted separately (i.e., to prevent sharing of HABITS material with home visitors assigned to deliver the control arm).

5.3 STUDY INTERVENTION COMPLIANCE

Home visitors randomized to deliver the HABITS intervention will complete a weekly checklist documenting all study-related intervention contacts with participants. As part of these checklists, home visitors will report the type of contact (home visit in-person, home visit by telephone, home visit by video call, or weekly check-in between home visits). For each home visit completed, home visitors will report the topics discussed and time spent discussing each topic.

6 STUDY INTERVENTION DISCONTINUATION AND SUBJECT DISCONTINUATION/WITHDRAWAL

6.1 DISCONTINUATION OF STUDY INTERVENTION

Participants will continue to receive the study intervention for the 12-month trial, as long as they remain in the home visiting program. The study intervention may be discontinued for a participant if a clinical adverse event (AE) or other medical condition or situation occurs such that continued participation in the study intervention would not be in the best interest of the subject.

6.2 SUBJECT DISCONTINUATION/WITHDRAWAL FROM THE STUDY

Subjects are free to withdraw from participation in the study at any time upon request. An investigator may discontinue or withdraw a subject from the study for the following reasons:

- Significant study intervention non-compliance
- If any clinical adverse event (AE) or other medical condition or situation occurs such that continued participation in the study would not be in the best interest of the subject

Subjects who sign the informed consent form and are randomized but do not receive the study intervention may be replaced. Subjects who sign the informed consent form, and are randomized and receive the study intervention, and subsequently withdraw, or are withdrawn or discontinued from the study, will not be replaced.

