1 PROTOCOL SUMMARY

1.1 SYNOPSIS

Title:	Leveraging Ongoing Home Visitation Programs to Address Obesity Disparities Among Underserved, Low-Income Mothers and Children (Obesity Health Disparities Research Center)
Study Description:	This two-arm, parallel, randomized controlled trial (RCT) tests the effectiveness of a simple obesity intervention (HABITS) delivered as part of ongoing home visiting services, compared to the existing home visiting services without obesity-related content on mothers' and children's obesity risks.
Objectives:	The objectives of the study are to compare the effects of treatment on children and primary caregivers' weight outcomes at 6 and 12 months, and to compare the effects of treatment on maternal feeding practices, habit strength of targeted behaviors, and features of the household environment relevant to targeted behaviors at 6 and 12 months.
Endpoints:	The primary endpoint is caregiver and child weight at 12-months
Study Population:	Participants will be 148 mothers (>50% African American; 100% low income) and their children (0–5yo at baseline) enrolled in a home visiting program in central Alabama.
Phase:	N/A
Description of Study Intervention:	The HABITS intervention focuses on habit formation and modifications of food and activity cues in the home to support habit formation. Habit formation is focused on improving five behaviors: 1) fruits/vegetables, 2) fried foods, 3) sugar-sweetened beverages, 4) physical activity and 5) self-monitoring.
Study Duration:	12-months
Subject Duration:	12-months

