3 STUDY DESIGN

3.1 OVERALL DESIGN

This is a cluster randomized trial in which home visitors (n=18 anticipated) employed by our partner (First Teach Home Visiting Program) will be randomly assigned to deliver the home visiting standard curriculum with or without HABITS (n=9 home visitors in each arm).

Caregivers with a child 0-5 years of age who are enrolled in the First Teacher Home Visiting program and who have completed their initial 90-day home visiting program benchmark testing will constitute our initial recruitment pool (>50% African American, 40% White, <10% other/multiple race). First Teacher Home Visiting Program enrolls caregivers with young children in their free and voluntary services through community outreach. In order to be eligible for home visiting services, families must have a social risk factor such as poverty, social isolation, lack of material and social support, lack of transportation and limited education and literacy.

Home visitors will approach their families who are potentially eligible to introduce the study, gauge interest, and screen interested families for eligibility. Designated study staff determine of families are eligible based on the completed screening form and inclusion/exclusion criteria. Home visitors are informed of family's eligibility and notify the family. Eligible families are then introduced to a blinded study assessment worker who schedules the enrollment and baseline visit.

Assessment workers (who are distinct from home visitors and masked to group assignment) will be responsible for completing informed consent, enrolling caregiver-child dyads into the study, and completing Visit 1 (baseline), Visit 2 (6-month), and Visit 3 (12-month) assessments.

After completing Visit 1 (baseline) assessment procedures, families will be told by their home visitor which study arm they have been allocated to, for those in the HABITS intervention arm (i.e., home visiting standard curriculum with HABITS) will begin receiving the HABITS intervention at their home visits for 12-months.

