4 STUDY POPULATION

4.1 INCLUSION CRITERIA

Families enrolled in home visiting will be invited to participate in the study, with limited exclusion criteria. Caregiver-child dyads will be eligible to participate regardless of weight status because the targeted health behaviors are relevant and beneficial for all caregivers and children. Improvements in maternal behaviors (regardless of weight status) may further reduce children's obesity risk. To be included, caregiver-child dyads will have to meet the following inclusion criteria:

- Caregiver enrolling in the trial is 18 years of age or older
- Child is 0-5 years of age
- Child has at least 1 year of eligibility remaining in the home visiting program
- Family has completed their first 90-days in the home visiting program

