5 STUDY INTERVENTION

5.1 STUDY INTERVENTION(S) ADMINISTRATION

5.1.1 STUDY INTERVENTION DESCRIPTION

Table 1 outlines the components of the two study arms.

Table 1. Components of each study arm	Standard home visiting (Control Group)	Standard home visiting + HABITS (Intervention Group)
Early childhood education and school readiness	X	X
Parenting	X	X
Socioemotional development (e.g., regulate emotion & behavior, develop empathy)	X	X
Physical development (e.g., immunization; motor skills)	X	X
Limit fried foods		X
Limit sugar-sweetened beverages		X
Increase daily steps		X
Increase non-starchy vegetables and fruits		X
Self-monitoring of weight and target behaviors (caregivers only)		X

Standard home visiting curriculum. Our partner home visiting program, First Teacher Home Visiting Program meets the Department of Health and Human Services (DHHS) criteria for an evidence-based early childhood home visiting service delivery model (<http://homvee.acf.hhs.gov>). Caregivers and children receive monthly or bi-monthly visits and they are provided with a set of carefully developed curriculum, books and materials designed to strengthen children's cognitive skills, early literacy skills, social/emotional and physical development. These voluntary services are free of charge for mothers and children (ages 0-5 years) most at risk of disparities because of poverty, social isolation, lack of material and social support, lack of transportation and limited education and literacy.

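### Section 6.2 lets dyads that do not receive the study intervention be replaced after allocation; this would act mostly in the HABITS arm, and nothing says replaced dyads stay in the analysis

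*Combined protocol and SAP*

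**What the plan says.** Section 6.2 sets the rule: "Subjects who sign the informed consent form and are randomized but do not receive the study intervention may be replaced". Subjects who do receive the intervention and later withdraw "or are withdrawn or discontinued from the study, will not be replaced".

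Four other places bear on how it works:

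- **Allocation.** Section 5.2 randomises 18 home visitors, nine per arm. A dyad takes the arm of its home visitor.
- **Disclosure.** Under Section 3.1, once Visit 1 is done, "families will be told by their home visitor which study arm they have been allocated to".
- **Prior exposure.** Section 4.1 requires: "Family has completed their first 90-days in the home visiting program".
- **Records of receipt.** Section 5.3 states: "Home visitors randomized to deliver the HABITS intervention will complete a weekly checklist documenting all study-related intervention contacts with participants". It asks for no matching checklist in the control arm.

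The term on which the rule turns is used in two ways. The synopsis row describing the study intervention reads: "The HABITS intervention focuses on habit formation and modifications of food and activity cues in the home to support habit formation". Section 5.1.1, headed as the description of the study intervention, covers both arms: "Table 1 outlines the components of the two study arms".

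Section 8.3 and its subsections specify mixed models with a home-visitor random effect, and multiple imputation or full information maximum likelihood for missing data. They define no analysis set, state no as-allocated principle, and do not mention replaced dyads.

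**The concern.** Replacement depends on something that happens after allocation and after the family knows its arm. A family told that it is in HABITS can decline the new content or never be reached with it. A control family continues a service it already has, so it has little comparable opportunity not to start.

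Any replacement would be recruited by a home visitor whose arm is already fixed. Section 3.1 gives home visitors the tasks of approaching families, gauging interest and screening. By the time a family has failed to start, its home visitor has already announced the arm.

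If the replaced dyad then leaves the dataset, the HABITS arm tends towards families who start, while the control arm keeps those who would not have started. Motivation and household stability could plausibly affect weight change, so the primary comparison could be biased. A larger sample would not reduce that bias, and the missing-data methods cannot act on dyads that are no longer in the dataset.

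**Working it through.** **1. The plan's own figure.** Section 8.2 gives 59 dyads per group for 80% power to detect 0.53 SD, two-sided α = 0.05. The exact t-test needs 57 per group, and power at 59 is 81.5%, so the figure reproduces closely. With 15% attrition, 59 / 0.85 = 69.4, or 70 per group and 140 in total, as stated.

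**2. In which arm the rule acts.**

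| Meaning of study intervention | Control dyad | HABITS dyad |
|---|---|---|
| HABITS (synopsis) | Never receives it, so the rule is undefined: literally, every control dyad is replaceable | Fails if it gets no HABITS content |
| Either arm's curriculum (5.1.1) | Fails only by leaving a service already used for 90 days | Fails the same way, or by not getting the new content |

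Both readings put most usable replacements in HABITS. Neither confines the rule to HABITS.

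**3. Bias if replaced dyads are dropped.** Let f be the share of HABITS dyads replaced and d the difference in mean weight change between starters and non-starters, in SD. Suppose the control arm keeps the same share f of would-be non-starters and replacements resemble starters. With no true effect, the expected difference between arms is f × d. Both inputs are assumptions.

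| f | d = 0.3 | d = 0.5 | d = 0.7 |
|---|---|---|---|
| 5% | 0.015 | 0.025 | 0.035 |
| 10% | 0.030 | 0.050 | 0.070 |
| 15% | 0.045 | 0.075 | 0.105 |

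As a share of the planning effect: 0.015 / 0.53 = 2.8% and 0.105 / 0.53 = 19.8%.

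Type I error with bias b is 1 − Φ(1.96 − b/SE) + Φ(−1.96 − b/SE), where SE = √(2/59) = 0.184 SD and clustering is ignored. For b = 0.05, b/SE = 0.27 and the error is 5.8%. Over a wider assumed range (f = 5–20%, d = 0.25–1.0 SD), the bias is 0.0125–0.20 SD and the error 5.1–19.2%.

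**4. Power if every allocated dyad is kept.** If non-starters gain nothing, the effect becomes 0.53 × (1 − f). With 59 analysed per group and no clustering:

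| f | Effect (SD) | Power | Analysed per group for 80% |
|---|---|---|---|
| 5% | 0.504 | 77.4% | 63 |
| 10% | 0.477 | 72.9% | 70 |
| 15% | 0.451 | 68.0% | 79 |

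**5. Whether the planned numbers absorb this.** The synopsis gives 148 dyads, or 74 per group; 74 × 0.85 = 62.9 analysed. That meets the 5% row only, and only if clustering is ignored. Applying the plan's own inflation to 118, with m = 118/18 = 6.56, gives IF = 1 + 5.56 × 0.01 = 1.056, and 118 × 1.056 / 0.85 = 146.5. Clustering therefore accounts for nearly all of the margin between 140 and 148.

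**The case against.** A reader might infer that the rule can operate only in the HABITS arm and that it removes non-starters from the trial. The documents support neither. Section 6.2 names no arm. Section 5.1.1 uses the term for both arms, and Section 6.1 speaks of participants continuing the study intervention while they remain in home visiting, again without limiting it to one arm. A control family that left home visiting straight after Visit 1 could therefore qualify. The wording is also permissive and may concern accrual alone: nothing says that follow-up stops or data are discarded. If replaced dyads stay in the analysis, the rule only adds dyads and f × d does not apply.

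The number replaced may also be small. Replacement ends once the intervention is received, Section 5.1.2 has visits at least monthly and usually twice monthly with remote contact allowed, and families have consented to a described intervention after 90 days in the service. Section 2.3.1 reports that participants were 27% less likely to discontinue home visiting with the combined curriculum in preliminary work. That concerns retention and says nothing direct about starting, but it gives no support for a high refusal rate.

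All of this stands against the stronger reading and the upper end of the range. The remaining defect is that replacement is conditioned on a post-allocation event, is undefined for controls on one reading, and has no analysis-set rule to make it harmless.

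**Conclusion.** The concern holds in limited form. Section 6.2 permits replacement on a criterion that is met or missed after families know their arm. It would act mostly in HABITS, through recruiters whose arm is fixed, and the analysis plan does not secure replaced dyads for follow-up or analysis. Whether bias arises depends on how the rule is applied, and the documents do not say.

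If replaced dyads are dropped, an illustrative bias is 0.015–0.105 SD, or 3–20% of the planning effect. This rests on assumed values of f and d, on an equal share of would-be non-starters in both arms, and on replacements resembling starters. A direction favouring HABITS is plausible but not proven. The point is a cheap improvement that should be made; it does not show that the comparison is already compromised.

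**What to change.** Amend Section 6.2, with a matching sentence in Section 8.3, to say that:

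- every dyad with consent and a completed Visit 1 is followed and analysed under its home visitor's allocation, whether or not HABITS content is received;
- no dyad is replaced after allocation is disclosed, or, if later enrolment is wanted, any such dyad is additional and never substitutes for another;
- non-starters are reported by arm. Visit dates recorded in both arms (Section 5.1.2) would give families with no completed visit after Visit 1, and the Section 5.3 checklist would give HABITS families with no intervention contact.

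The text change is a short amendment. The statistical cost is dilution: at 5%, 10% and 15% non-starters who gain nothing, power with 59 analysed per group falls from 81.5% to about 77%, 73% and 68%. Neither the 148 in the synopsis nor the 15% attrition allowance clearly absorbs this. An attrition allowance makes up for missing outcomes and does not offset a smaller effect. The loss should be acknowledged in Section 8.2 as the price of an as-allocated estimate.

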6.3 LOST TO FOLLOW-UP

A subject will be considered lost to follow-up if he or she fails to return for 2 scheduled visits and is unable to be contacted by the study staff.

The following actions must be taken if a subject fails to be available for a required study visit:

- The site will attempt to contact the subject and reschedule the missed visit and counsel the subject on the importance of maintaining the assigned visit schedule and ascertain if the subject wishes to and/or should continue in the study.
- Before a subject is deemed lost to follow-up, the investigator or designee will make every effort to regain contact with the subject (where possible, 3 telephone calls and, if necessary, a certified letter to the subject's last known mailing address or local equivalent methods). These contact attempts should be documented in the subject's study file.
- Should the subject continue to be unreachable, he or she will be considered to have withdrawn from the study with a primary reason of lost to follow-up.

7 STUDY ASSESSMENTS AND PROCEDURES

7.1 STUDY ASSESSMENTS

All caregiver-child dyads in the study will complete three (3) assessments: 1) Visit 1 (baseline) at the start of the study, 2) after 6 months (Visit 2), and 3) after 12 months (Visit 3). Blinded assessment staff (assessment workers) will work with families to complete these assessments. Assessments may be done completely in-person at a family's home, a combination of over the phone and in-person, or all remotely with no in-person, physical contact. The visits will include surveys and other measures described below:

- Intake and Demographics Survey (Visit 1 only): Asks questions about age, education, income level, race, medical history.
- The Physical Activity Readiness Questionnaire [PAR-Q] (Visits 1 and 2): Assesses health and ability to do physical activities. If there are any concerns about a caregiver's ability to participate in the walking and movement section of the Habits program, they may be asked to see a doctor about their health before taking part in this section of the program. They will still be able to participate in other parts of the program.⁷⁵
- Behavior Rating Inventory of Executive Function for Adults [BRIEF-A] (All 3 visits): Caregivers will complete this validated questionnaire that asks about attention and how they react to different situations.⁷⁶
- Medical Changes Survey: (Visits 2 and 3): Caregivers will be asked to report any medical or health changes that might have happened since the caregiver and child first started the study.

- Self-Report Behavioural Automaticity Index [SRBAI] (All 3 visits): A four-item automaticity scale that assesses automaticity of HABITS target behaviors for the caregiver and for the caregiver encouraging the child to engage in each target behavior.⁷⁷
- Weight measurements (All 3 visits): Mothers' and child's weight will be measured in duplicate using an electronic scale (Model BWB-800S, Tanita, Portage, MI) according to standard procedures.⁷⁸
- Height measurements (All 3 visits): Caregiver height will be measured in duplicate using a portable stadiometer (Seca 213, Perspective Enterprises) according to standard procedures.⁷⁸ When a height measurement is not possible (due to COVID-19 restrictions), caregivers will be asked to self-report their height.
- Patient Health Questionnaire-8 [PHQ-8] (All 3 visits): Assesses caregiver's thoughts and feelings over the last two weeks.⁷⁹
- Food and Activity Frequency Survey (All 3 visits): To best capture maternal feeding practices related to behaviors targeted by HABITS, mothers will complete modified versions of the Children's Dietary Questionnaire⁸⁰ and Diet and Behavior Questionnaire (DBQ)⁸¹ of the National Health and Nutrition Examination Survey. These instruments will be modified to focus on the eating behaviors targeted by HABITS: SSB, fried foods, and fruits and vegetables.
- Home Food and Activity Environment Assessment (All 3 visits): A modified version of the Home Food Assessment (HFA) and Home-Inventory Describing Eating and Activity Development (Home-IDEA) adapted to HABITS target behaviors will be used by assessment workers to assess accessibility and visibility of fruits, vegetables, fried food, SSB, and activity-related stimuli/cues (e.g., stroller). Items are coded as "yes" or "no" on availability. Both instruments have been validated in the homes of families with children. The Home Food and Activity Environment Assessment may be completed in-person in the family's home or (if needed to abide by COVID-19 safety guidelines) by telephone.⁸²⁻⁸⁵

Caregiver-Child benchmark data and home visit completion data will be collected from the First Teacher Home Visiting Program to ensure the study does not affect family services. For this, First Teacher Home Visiting Program will provide us with their assessments that are done as part of the standard First Teacher Home Visiting Program yearly evaluations. These questionnaires are not part of our study assessments.

7.2 ADVERSE EVENTS AND SERIOUS ADVERSE EVENTS

7.2.1 DEFINITION OF ADVERSE EVENTS (AE)

Adverse event means any untoward medical occurrence associated with the use of an intervention in humans, whether or not considered intervention-related (21 CFR 312.32 (a)).

7.2.2 DEFINITION OF SERIOUS ADVERSE EVENTS (SAE)

An adverse event (AE) is considered "serious" if, in the view of either the investigator or sponsor, it results in any of the following outcomes:

- Death
- A life-threatening adverse event (of note, the term "life-threatening" refers to an event in which the subject was at risk of death at the time of the event, rather than to an event which hypothetically might have caused death if it were more severe)
- inpatient hospitalization or prolongation of existing hospitalization

- a persistent or significant incapacity or substantial disruption of the ability to conduct normal life functions
- or a congenital anomaly/birth defect.

Important medical events that may not result in death, be life-threatening, or require hospitalization may be considered serious when, based upon appropriate medical judgment, they may jeopardize the subject and may require medical or surgical intervention to prevent one of the outcomes listed in this definition. Examples of such medical events include allergic bronchospasm requiring intensive treatment in an emergency room or at home, blood dyscrasias or convulsions that do not result in inpatient hospitalization, or the development of drug dependency or drug abuse.

